• Describe the study, providing detail regarding the study intervention (drug, device, physical procedures, manipulation of the subject or the subject's environment, etc.). Discuss justifications for placebo control, discontinuation or delay of standard therapies, and washout periods if applicable. Identify procedures, tests and interventions performed exclusively for research purposes or more

frequently than standard of care. Include alternative therapies, concurrent therapies discontinued per protocol, risk benefit ratio, and use of tissue/specimens. Discuss monitoring during washout periods if applicable. Include brief description of follow-up, if any.

The entire study (Aims 1-3) will enroll up to 60 participants. While we anticipate that the screening blood draw will yield a number of screen failures, we expect that approximately 20-25 subjects will complete AIM-2 and 15-20 will complete AIM-3 of the study protocol. All study visits and procedures will take place in the Human Physiology Testing Core shared resource facilities located at the Duke Center for Living campus.

AIM-2

Approximately 20-25 healthy subjects will complete Aim-2 of the study and these participants will have three study visits – a baseline consent visit, and two infusion procedures.

Visit 1: The consent visit will take place at the Duke Center for Living and will last approximately two hours. If the participant has given prior verbal consent during the phone screening process, they will fast (nothing but water) for 12 hours before this visit and their body mass index (composed of weight and height measures) will be checked to see if it falls within the inclusion range. Daily medications may be taken. We will explain the study and the consent form in detail. Upon signing the consent form, a sample of blood (one teaspoon) will be drawn to measure hemoglobin A1c (HbA1c), fasting glucose level, kidney function (i.e. eGFR) and blood count (i.e. hematocrit) are within normal limits to ensure that the participant meets inclusion criteria. If these values are within the range listed below for the appropriate cohort, the participant will be scheduled for Visit 2.

If a woman is of childbearing potential, a blood (using one teaspoon of blood drawn by a needle-stick) pregnancy test will be conducted and it must be negative prior to continuation in this study.

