Subjects will have two intravenous catheters placed, one in each arm: 1) for blood drawing, and 2) for the infusion of test materials. The arm for blood draws will be heated to maintain blood flow and arterialize venous blood. Four (4.0 ml) fasting blood samples will be taken at -15, -10, -5 and 0 minutes and then a variable infusion of 20% dextrose will begin to clamp the blood glucose at basal +3 mM for 120 minutes. This hyperglycemic clamp will be stabilized over 60 minutes and 4.0 ml blood samples will be taken every 5-10 minutes during this period to establish baseline insulin secretion and active GLP-1 levels. During these visits, participants will receive an infusion of Exendin-9 (750 pmol/kg/min) between the 60 and 120 minute time-points of the clamp procedure. For consistency, blood draws (4.0 ml) will occur every 5-10 minutes between the 60 and 120 minute time-points of both visit 2 and 3. Upon completion of the final 60-minute interval for the Ex-9 infusion, both the infusion and clamp procedures will be complete. One additional blood sample (1 ml) will be drawn post the assessment to be tested immediately with the YSI glucose analyzer to ensure glucose levels are within normal limits. **Visit 3** will occur at least one week later and will be a repeat infusion procedure identical to **Visit 2**. The total amount of blood collected during each of these visits will be a maximum of ~141 ml (~9.5 Tbsp).

We will aim to complete studies in 10-15 subjects before and after approximately one week of dexamethasone(Dex) treatment to induce insulin resistance. Insulin resistance in response to a short-course (4 mg daily) of supraphysiologic glucocorticoids is an established research procedure and is completely reversible over the course of exposure we are proposing. However, the rate of reversal is variable among subjects preventing a straight counter-balanced allocation to treatment (i.e. half of subjects getting Dex before the first study and half before the second). Therefore we will enroll 6-10 subjects as controls for effects of time and repeat testing. These individuals will have identical clamps with no dexamethasone at approximately 1 week intervals and will be determined at random by study staff.

AIM-3

Approximately 15-20 subjects will complete AIM-3 of the study and these participants will have two study visits – a baseline consent visit, and one infusion procedures.

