Visit 1: Visit 1 is a baseline study visit during which the following will take place:

- Potential subjects will review and sign the consent form with study staff.
- The participant's current medications will be recorded for review by study staff.
- A screening blood draw will be obtained to measure fasting glucose, HbA1c, hematocrit, and eGFR.

If a woman is of childbearing potential, a blood (using one teaspoon of blood drawn by a needle-stick) pregnancy test will be conducted and it must be negative prior to continuation in this study.

Visit 2: Similar to Aim 2, each participant will have a 4-hour hyperglycemic clamp procedure with the addition of the GLP-1 receptor antagonist Exendin-9 (Ex-9) to determine the *fasting GLP-1 effect*. The participants will receive an infusion of Ex-9 beginning at the 60-minute mark of the clamp procedure. Throughout the glucose infusion during visit-2, 1 ml blood samples will be taken every 5-10 minutes beginning at the -15 minute time-point and continue until the end of the 120 minute procedure. These samples will be tested immediately with a YSI glucose analyzer and the values used to adjust the glucose infusion rate to maintain stable blood glucose concentrations (a glucose clamp) throughout the experiment.

Subjects will report to the Duke Center for Living after a 12-hour fast. Study staff will obtain the participant's current body weight. At Visit-2 a skin test to confirm they do not have any sensitivity to the Ex-9 investigational compound that will be used during the infusion will be administered. The skin test is specified by the FDA as a precaution for immediate hypersensitivity; 5 ng of Ex-9 is injected intradermally and subjects are monitored for 30 minutes for a wheal/flare reaction. This skin test must be negative in order to continue with the study testing.

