Subjects will have two intravenous catheters placed, one in each arm: 1) for blood drawing, and 2) for the infusion of test materials. The arm for blood draws will be heated to maintain blood flow and arterialize venous blood. Four (4.0 ml) fasting blood samples will be taken at -15, -10, -5 and 0 minutes and then a variable infusion of 20% dextrose will begin to clamp the blood glucose at basal +3 mM for 120 minutes. This hyperglycemic clamp will be stabilized over 60 minutes and 4.0 ml blood samples will be taken every 5-10 minutes during this period to establish baseline insulin secretion and active GLP-1 levels. During these visits, participants will receive an infusion of Exendin-9 (750 pmol/kg/min) between the 60 and 120 minute time-points of the clamp procedure. For consistency, blood draws (4.0 ml) will occur every 5-10 minutes between the 60 and 120 minute time-points. Upon completion of the final 60-minute interval for the Ex-9 infusion, both the infusion and clamp procedures will be complete. One additional blood sample (1 ml) will be drawn post the assessment to be tested immediately with the YSI glucose analyzer to ensure glucose levels are within normal limits. The total amount of blood collected during this visit will be a maximum of ~141 ml (~9.5 Tbsp).

Selection of Subjects

• List inclusion/exclusion criteria and how subjects will be identified.

AIM-2 SELECTION OF HEALTHY SUBJECTS: Study recruitment will occur primarily through advertisements via Duke websites, as well as local newspapers (e.g. Independent, Durham Herald, Duke Chronicle); and social media venues (e.g. DMPI Facebook page, Instagram), will be used as well as use of our Duke Health and Exercise Research Trials registry. Study recruitment will also take place at public venues (e.g. Duke Farmer's Market or Community Health Fairs). Potential subjects for this study will be directed to contact the study staff to obtain more information about the study, if interested. Study participants will also be recruited using flyers posted across the Durham VAMC hospital and Duke hospital /clinic facilities, inviting interested individuals to contact the study recruitment coordinator for additional information.

Inclusion criteria:

- Healthy adults age 20-45 years
- Male or female
- Body Mass Index (BMI) ≤ 35.0 kg/m²
- HbA1c ≤ 5.7%

Ability to speak and understand English

Exclusion criteria:

- Uncontrolled high blood pressure

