- Diabetes or use of diabetes medications such as insulin or metformin
- Evidence of active heart disease or heart failure
- Lung disease or COPD
- Malabsorptive GI disease, such as celiac disease, or gastric bypass
- Significant hepatic disease
- Kidney disease or renal insufficiency (eGFR < 60 mL/kg/min)
- Untreated anemia (hematocrit < 34%) as measured at screening visit
- Pregnant females
- Active substance abuse
- Chronic use of oral steroid medications such as prednisone and hydrocortisone
- Apparent sensitivity to any of the study peptides as determined by the skin test
- Diagnosis or h/o PTSD
- · Active mental health disorders such as depression, or as a result of Traumatic Brain Injury (TBI)

Exclusion criteria will primarily be identified by way of a phone screen process conducted by the coordinator, however medical record review may be used to confirm the absence of a diabetes mellitus diagnosis or other medical conditions listed as exclusion criteria.

AIM-3 SELECTION OF SUBJECTS:

Selection of Non-Diabetic Subjects: Study recruitment will occur primarily through advertisements via Duke websites, as well as local newspapers (e.g. Independent, Durham Herald, Duke Chronicle); and social media venues (e.g. DMPI Facebook page, Instagram) will be used as well as use of our Duke Health and Exercise Research Trials registry. Study recruitment will also take place at public venues (e.g. Duke Farmer's Market or Community Health Fairs). Potential subjects for this study will be directed to contact the study staff to obtain more information about the study, if interested.

Study participants will also be recruited using flyers posted across the Durham VAMC hospital and Duke hospital/clinic facilities, inviting interested individuals to contact the study recruitment coordinator for more information. In addition, the VA Informatics and Computing Infrastructure (VINCI) will be used to identify potential subjects that meet the inclusion criteria. The study staff will pre-screen subjects listed on the VINCI reports in CPRS and contact those subjects identified to meet the inclusion criteria. Recruitment may occur through the VA Endocrinology practice and primary care clinics.

Inclusion criteria - Non-Diabetic Subjects:

- Adults age 18-65 years
- Male or female
- Body Mass Index (BMI) 25-40 kg/m²
- HbA1c \leq 6.5% as measured at screening visit
- No Diabetes or use of diabetes medications such as insulin or metformin
- Ability to speak and understand English

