- The risks from infusion of micromolar amounts of exendin-(9-39) are remote. In rare cases, nausea and vomiting have been reported as possible side effects for Ex-9. The IND has been obtained from the FDA for the infusion of exendin-(9-39) [#65837] into humans. The Principal Investigator for the present study has used this peptide in several previous studies, in doses similar to those described in this application, with no attributable adverse effects observed. Allergic reactions to synthetic peptides are possible; therefore skin testing will be performed on each subject to assess sensitivity prior to undergoing any clamp procedures. All peptides will be synthesized to GMP standards and documented sterile and pyrogen free.
- The maximum amount of blood to be withdrawn during any one of these infusion procedures is approximately 141 ml and does not constitute an undue risk in persons with normal hematocrits.
- At study entry, women of child-bearing potential will have a serum pregnancy test. The pregnancy test must be negative before the subject can undergo any study testing.
- AIM-2: Some side effects of dexamethasone may include upset stomach, headache, dizziness, insomnia, restlessness, increased appetite or weight gain may occur.

This is not a complete list of possible side effects. If the participant notices other effects not listed above, they will be advised to contact the study physician.

Costs to the Subject

• Describe and justify any costs that the subject will incur as a result of participation; ordinarily, subjects should not be expected to pay for research without receiving direct benefit.

There will be no costs to participants for any of the treatments or testing done as part of this research study. Immediate necessary care is available if an individual is injured because of participation in a research project. However, there is no provision for free medical care or for monetary compensation for such injury. During this study, hospitalizations or additional care beyond the scope of this study will be the responsibility of patients and/or their insurance company.

Data Analysis & Statistical Considerations

Describe endpoints and power calculations. Provide a detailed description of how study data will be
analyzed, including statistical methods used, and how ineligible subjects will be handled and which
subjects will be included for analysis. Include planned sample size justification. Provide estimated time

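### The blood-loss rationale covers only people with a normal hematocrit, but the Aim-3 exclusion, read literally, lets in treated anemia below 34%, and in Aim 2 the same line conflicts with the screening step

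*Combined protocol and SAP*

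**What the plan says.** Four places in the combined protocol and SAP bear on who may give the blood.

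- **Risk/Benefit Assessment.** The maximum for any one infusion procedure is "approximately 141 ml and does not constitute an undue risk in persons with normal hematocrits". This is the only safety argument offered for the volume drawn.
- **Selection of Subjects, exclusion lists.** Aim 2 and Aim 3 (the list for all subjects) use identical wording: "Untreated anemia (hematocrit < 34%) as measured at screening visit".
- **Design & Procedures, AIM-2, Visit 1.** Screening blood is drawn to check that "kidney function (i.e. eGFR) and blood count (i.e. hematocrit) are within normal limits to ensure that the participant meets inclusion criteria". The text continues: "If these values are within the range listed below for the appropriate cohort, the participant will be scheduled for Visit 2". The Aim-2 population is also described as "Healthy adults age 20-45 years".
- **Design & Procedures, AIM-3, Visit 1.** The corresponding text is only: "A screening blood draw will be obtained to measure fasting glucose, HbA1c, hematocrit, and eGFR". It does not ask for a normal result and does not make the infusion visit depend on one. The Aim-3 text likens its Visit 2 to Aim 2, but not its Visit 1.

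No section defines a normal hematocrit or says that 34% is its lower limit.

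**The concern.** A safety rationale should cover everyone the criteria admit. Here the rationale is tied to a normal hematocrit, while the exclusion is tied to a low hematocrit together with absence of treatment. The two differ for a volunteer under treatment for anemia whose screening value is still below 34%. The study offers participants no benefit, so its account of how risk is contained carries more weight than usual.

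Aim 3 is the firmer ground. It takes adults aged 18 to 65, including people with type 2 diabetes, it has no healthy-adult criterion, and the exclusion line is its only hematocrit restriction. In Aim 2 the issue is consistency: the visit description and the exclusion list can give opposite answers to the same laboratory result.

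No endpoint, analysis or sample size is affected.

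**Working it through.** **Step 1: reproduce the stated volume.** The inputs come from Design & Procedures, AIM-2 Visits 2 and 3; AIM-3 Visit 2 has the same schedule. The maximum arises at the densest permitted spacing, every 5 minutes.

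- 4.0 ml samples, fasting: "Four (4.0 ml) fasting blood samples will be taken at -15, -10, -5 and 0 minutes", so 4 samples.
- 4.0 ml samples, clamp: 120 / 5 = 24 samples.
- 4.0 ml subtotal: (4 + 24) × 4.0 = 112 ml.
- 1 ml glucose samples from −15 to 120 minutes: (120 + 15) / 5 + 1 = 28 samples, or 28 ml.
- One 1 ml sample after the procedure: 1 ml.
- Total: 112 + 28 + 1 = **141 ml**. At an assumed 14.79 ml per tablespoon, 141 / 14.79 = 9.5 tablespoons. Both agree with the protocol.

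At 10-minute spacing after the four fasting draws, the total is (4 + 12) × 4.0 + (4 + 12) × 1 + 1 = 64 + 16 + 1 = 81 ml. The range per procedure is therefore 81 to 141 ml.

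**Step 2: volume by aim.** Aim 3 has one procedure, up to 141 ml. Aim 2 has two, at least one week apart, up to 2 × 141 = 282 ml. Screening blood is additional in both.

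**Step 3: apply each passage to the same screening result.** Assumption: a value below 34% is not normal. The documents do not say so, but they use that figure to mark anemia.

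| Screening result | Exclusion line, literal reading | Exclusion line, read by value alone | Aim-2 Visit 1 text | Aim-3 Visit 1 text | Risk statement |
|---|---|---|---|---|---|
| Below 34%, untreated | Excluded | Excluded | Not normal | No rule | Not covered |
| Below 34%, treated | **Not excluded** | Excluded | Not normal, but refers on to the listed range | No rule | **Not covered** |
| 34% or above | Not excluded | Not excluded | Depends on the undefined normal range | No rule | Depends on the undefined normal range |

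The second row is the problem. In Aim 3 the Visit 1 text adds nothing, so the literal exclusion line decides and the volunteer may proceed without being covered by the risk statement. In Aim 2 the Visit 1 text first asks for a normal value and then sends staff to the lists, where the only hematocrit figure is the 34% line with its treatment qualifier. The two halves of that instruction can disagree.

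**The case against.** The strongest reply is that the passages can be read as one rule. The parenthesis and the reference to the screening measurement may be there to define the excluded condition, so that anyone below 34% is out. The Aim-2 text points forward to a listed range, and 34% is the only hematocrit figure that follows. With no normal range given, nothing proves that the risk statement has a different limit in mind. That reading is tenable, but it leaves the word *untreated* with no function. A safety criterion with two reasonable readings and opposite outcomes still needs rewording.

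The reply does succeed against several stronger claims that a reader might infer:

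- **That Aim 2 leaves an open route to two draws for people outside the risk statement.** It does not. The Aim-2 Visit 1 text asks for a normal hematocrit and makes Visit 2 depend on the measured values, and the population is described as healthy. What remains in Aim 2 is an inconsistency.
- **That 282 ml over two visits is an error or breaches a limit.** The documents set no cumulative limit. The risk statement openly counts one procedure, and the total is a simple doubling of disclosed figures. Consent pages are not in the text supplied, so nothing can be said about what participants are told of the total.
- **That different sites would decide differently.** All visits take place at one facility. The possible variation is between staff members or over time.

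**Conclusion.** The point holds in a limited form. In Aim 3, on a literal reading, a treated volunteer with a screening hematocrit below 34% could undergo the one procedure of up to 141 ml although the protocol's safety argument does not extend to that person. In Aim 2 the exclusion line and the Visit 1 text conflict, so the same result could be decided either way.

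This rests on the literal reading of the exclusion line and on the assumption that a value below 34% is not normal. The number affected cannot be derived from the documents. It is bounded by Aim-3 enrolment (15 to 20 expected completers) and may be zero. No participant is shown to have been exposed or harmed, and the volume itself is correctly stated. The correction is worth making because it decides who may undergo the draw and uses a measurement already taken.

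**What to change.** Reconcile five places: the AIM-2 Visit 1 text, the AIM-3 Visit 1 text, both exclusion lists, and the blood-loss statement in the Risk/Benefit Assessment. One hematocrit rule, applied to the screening value, should govern both aims and admit only people whom the risk statement covers. Alternatively, widen the risk statement to everyone the criteria admit and justify it. Whether treatment status should matter, and what the numeric limit is, are for the investigators to settle. The AIM-3 Visit 1 text should also say that scheduling the infusion depends on the result.

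Stating the Aim-2 two-visit maximum of about 282 ml beside the per-procedure figure would be a useful clarification, but it is optional.

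The cost is an amendment to wording, with no new test and no change to design or sample size. Depending on the rule chosen, an occasional treated volunteer may be lost.

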AIM-3 – The primary outcome measure for this study will be the fasting GLP-1 effect. This will be defined as the difference in steady state glucose-stimulated insulin secretion with and without Ex-9. The difference will be expressed as a percentage of glucose stimulated insulin secretion without Ex-9, and serve as the primary variable for comparison among the lean, obese and diabetes cohorts.

Research Summary

State your primary study objectives

AIM-2: Determine the role of basal GLP-1 action on the β -cell response to insulin resistance. Healthy subjects will have fasting GLP-1 action determined with GLP-1r blockade before and after induction of experimental insulin resistance. We hypothesize that fasting GLP-1 action will increase to compensate for experimental insulin resistance.

AIM-3: The primary outcome measure for this study will be the fasting GLP-1 effect. This will be defined as the difference in steady state glucose-stimulated insulin secretion with and without Ex-9.

State your secondary study objectives

Please select your research summary form:

Standard Research Summary Template

This is the regular (generic) research summary template which is required for all regular applications (unless your protocol fits under the other research summary templates in this category). Use of these instructions is helpful for ensuring that the research summary contains all necessary elements.

Standard Research Summary

Purpose of the Study

Objectives & hypotheses to be tested

This protocol is funded by the Veteran's Administration and being led by [name] [name] in the Division of Endocrinology and the Duke Molecular Physiology Institute. The study will address the following three specific aims:

- 1. Determine the roles of fasting GLP-1 concentrations and alpha-cell secretion on insulin release. The first part of this aim will determine the threshold plasma concentration of GLP-1 that increases insulin secretion to test the hypothesis that fasting levels of circulating GLP-1 are insufficient to mediate β -cell secretion. The second part of the aim will determine whether the insulin response to specific amino acids is dependent on the α -cell release of GLP-1.

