- 2. **Determine the role of basal GLP-1 action on the β-cell response to insulin resistance.** Heal thy subjects will have fasting GLP-1 action determined with GLP-1r blockade before and after induction of experimental insulin resistance. We hypothesize that fasting GLP-1 action will increase to compensate for experimental insulin resistance.
- 3. Determine the role of basal GLP-1 action on fasting glucose regulation in lean, obese, pre-diabetic and diabetic subjects. A cross sectional study of age-matched subjects across the spectrum of glucose tolerance will be used to test the hypothesis that fasting GLP-1 action increases as β-cell function declines. Groups of lean, obese, pre-diabetic and type 2 diabetic (T2DM) subjects will receive exedin-9 during a graded glucose infusion. We hypothesize that the relative effect of GLP-1r blockade on insulin secretion will be greater with progression from normal to T2DM.

Initially, this study was to address these three aims in sequential order such that the findings from Aim 1 would be used to further develop the protocol design and procedures for Aim 2, and similarly the findings from Aims 1 and 2 will strengthen the approach to Aim 3. To that end, [name] has been able to address Aim 1 by collecting and analyzing data from another study with a similar protocol design. This IRB amendment is being filed to address the procedures for both Aim 2 and Aim 3.

Background & Significance

• Should support the scientific aims of the research

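### Aim 3's primary comparison includes a lean cohort, but both Aim-3 inclusion lists require BMI 25-40, so that cohort is empty or undefined

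*Combined protocol and SAP*

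**What the plan says.** **Analysis.** The Research Abstract (AIM-3 paragraph) and Data Analysis & Statistical Considerations (AIM-3) both say that the fasting GLP-1 effect, as a percentage, will "serve as the primary variable for comparison among the lean, obese and diabetes cohorts". That is three cohorts.

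**Objective.** The third aim, in the Research Abstract and in Purpose of the Study, lists four: "Groups of lean, obese, pre-diabetic and type 2 diabetic (T2DM) subjects will receive exedin-9". It describes a cross-sectional study of "age-matched subjects across the spectrum of glucose tolerance".

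**Eligibility.** Selection of Subjects gives Aim 3 two inclusion lists, one for non-diabetic and one for T2DM subjects. Each carries the same BMI criterion, "Body Mass Index (BMI) 25-40" kg/m², and ages 18-65. The non-diabetic list allows HbA1c up to 6.5%. The T2DM list requires a diagnosis and HbA1c up to 7.5%.

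**Numbers.** Design & Procedures expects 15-20 Aim-3 completers and does not divide them by cohort. No sample-size calculation is given for Aim 3.

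**Aim 2, for comparison.** Its inclusion list reads "Healthy adults age 20-45 years", with BMI up to 35.0 and no lower limit, and HbA1c up to 5.7%. The Aim-3 clamp is described as follows: "Similar to Aim 2, each participant will have a 4-hour hyperglycemic clamp procedure".

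**The concern.** A cohort named in a primary comparison has to be one that the eligibility criteria can fill and the analysis can identify. Here the lean cohort appears in the analysis, while the only Aim-3 entry criteria start at a BMI of 25. Someone following the document exactly would reach the analysis with no lean subjects, or with a mixed non-diabetic group and no stated rule for dividing it.

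The same gap affects pre-diabetes. Such people can enter through the non-diabetic list and nothing excludes them from the analysis, yet the three-cohort comparison gives them no place and no threshold separates them from normal.

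What is at stake is which conclusions Aim 3 can support. In addition, if the lean/obese and normal/pre-diabetic divisions are not fixed beforehand, they could be chosen after the results are known. In a study of 15-20 people, moving one or two subjects between groups matters.

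**Working it through.** The core check is one of consistency, and the plan gives no Aim-3 figure to reproduce.

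**1. Group lists side by side**

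| Place | Groups |
|---|---|
| Third aim (Research Abstract; Purpose of the Study) | 4: lean, obese, pre-diabetic, T2DM |
| Primary comparison (Research Abstract; Data Analysis) | 3: lean, obese, diabetes |
| Aim-3 inclusion lists (Selection of Subjects) | 2: non-diabetic, T2DM |

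**2. Can the lean cohort be filled?** Both lists admit BMI 25 to 40, and exclusion criteria can only narrow that. The documents do not define lean, so two cases arise.
- Lean is BMI under 25 (assumption): the overlap with 25-40 is empty, giving 0 lean subjects among 15-20 completers.
- Lean uses some cut above 25: the cohort could exist, but no cut is stated, so lean and obese cannot be told apart within the one non-diabetic list.

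**3. Could Aim 2 supply it?** Aim 2 has no BMI floor, and its clamp and Ex-9 infusion match those of Aim 3. It plans 10-15 dexamethasone subjects, each with a clamp before treatment, and 6-10 controls: "These individuals will have identical clamps with no dexamethasone at approximately 1 week intervals". Subjects with at least one clamp without dexamethasone therefore number 10 + 6 = 16 to 15 + 10 = 25. How many would be lean is not stated, and nothing assigns them to Aim 3. Their ages are 20-45, against 18-65 in Aim 3.

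**4. Why the number of groups matters (context only).** Assume an equal split, since none is given, and an unadjusted two-sample t test between two groups at two-sided 0.05 with 80% power. The detectable difference *d*, in SD units, solves: power of a t test with 2*n* − 2 degrees of freedom and noncentrality *d*√(*n*/2) equals 0.80.

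| Groups | n per group (15 to 20 completers) | Detectable difference | Same, with error variance pooled over all groups |
|---|---|---|---|
| 2 | 15/2 = 7.5 to 20/2 = 10 | 1.57 to 1.32 SD | same |
| 3 | 15/3 = 5 to 20/3 = 6.7 | 2.02 to 1.68 SD | 1.93 to 1.63 SD |
| 4 | 15/4 = 3.75 to 20/4 = 5 | 2.51 to 2.02 SD | 2.25 to 1.89 SD |

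The last column replaces 2*n* − 2 by *N* − *k* degrees of freedom, where *N* is the number of completers and *k* the number of groups. The plan names no test for Aim 3, so both columns are assumptions. The contradiction in steps 1 and 2 does not depend on them.

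**The case against.** The strongest reply is that little of the science is lost. The stated hypothesis is that the relative effect of GLP-1 receptor blockade grows from normal to T2DM. That concerns glucose tolerance, not adiposity, and it can be examined within BMI 25-40. This stands, and it limits the seriousness of the point. It does not rescue the comparison that the plan names as primary, and the normal end of that progression also lacks a definition.

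A second reply is that Aim 2 was meant to provide the lean data. It admits BMI under 25 and uses the same procedure, the text says that earlier aims will strengthen the approach to Aim 3, and ages 20-45 lie inside 18-65, so matching on the overlap is feasible. This is a plausible intention, but no text states it. Subjects above 45 in the other cohorts would also have no lean counterpart.

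Third, choosing cohorts after seeing the data is a possibility and not something the document shows. BMI, HbA1c and fasting glucose come from before the clamp, and T2DM status rests on diagnosis. That is fair: the risk is confined to the lean/obese and normal/pre-diabetic cuts, which are the ones left open.

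Finally, the detectable differences assume separate t tests and an equal split. Pooling the error variance lowers the three- and four-group figures somewhat, without changing the picture.

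**Conclusion.** The concern holds. As written, Aim 3 cannot deliver its stated three-cohort primary comparison: the lean cohort has 0 eligible subjects if lean means BMI under 25 (an assumption, because the documents do not define it) and is undefined under any higher cut. A lean-versus-obese conclusion is not available. Overweight/obese non-diabetic versus T2DM, and a comparison across glucose tolerance within BMI 25-40, remain possible. The point should be fixed, but it does not invalidate the whole aim.

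**What to change.** Use one group list in the objective, the eligibility criteria and the analysis, by one of three routes:

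- **(a) Add a lean stratum** with a stated BMI range to the Aim-3 non-diabetic criteria, and state the lean/obese cut. This means an amended eligibility list and recruiting a new stratum within the 60-participant ceiling. If the 15-20 completers are spread over three or four filled groups instead of the two that can be filled now, the detectable pairwise difference rises from about 1.3-1.6 SD to 1.7-2.0 or 2.0-2.5 SD (separate t tests).
- **(b) State that lean data come from Aim-2 clamps without dexamethasone.** Say which subjects and which clamp are used, and how the age difference (20-45 against 18-65) is handled given the age-matched design. The cost is text only; the drawback is a younger cohort recruited under another aim.
- **(c) Remove lean** and limit the conclusion to overweight/obese non-diabetic versus T2DM. The cost is text only; the lean-versus-obese conclusion is given up.

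Routes (b) and (c) are the cheapest. Under any route, define the pre-diabetic group in advance or take it out of the objective. No new test is needed, because the Aim-3 Visit 1 text already provides the measurements: "A screening blood draw will be obtained to measure fasting glucose, HbA1c, hematocrit, and eGFR".
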